10.6.5 Relationship to IMP

The Investigator must assess the AE as either Related or Not Related to IMP. A suspected adverse reaction is defined as one in which there is a reasonable possibility that the drug caused the adverse event. Relatedness has to be assessed and reported from the first time the AE is being reported. When assessing the causal relationship of an AE to the IMP, the following should be taken into consideration:

Not related (unlikely)

The AE is not related to the IMP, which means the event:

- Does not follow a reasonable temporal sequence from IMP administration.
- Is readily explained by the patient's clinical state or by other modes of therapy administered to the patient.
- The AE is clearly not related to the IMP.

For AEs assessed as "Not Related", an alternative etiology should be stated detailing the more likely reason for AE.

Related (possible/probable)

The AE is related to the IMP, which means the event:

- Follows a reasonable temporal sequence from IMP administration.

- Abates spontaneously upon discontinuation of the IMP (de-challenge) without any curative treatment.
- Is confirmed by reappearance of the same reaction on repeat exposure (re-challenge).
- Cannot be reasonably explained by the known characteristics of the patient's clinical state or medical history.
- Alternative etiology should be provided for all AEs assessed as possible related to IMP

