¹⁰ If CSF sample is positive for abnormal cells or outside reference ranges for any of the following: 1. total protein 2. glucose 3. cell count, it must be repeated within 4 weeks of the sample at screening. If abnormal CSF glucose (CTCAE \geq Grade 2) is obtained, a fasting serum glucose is to be obtained at next patient visit. At week 26, the CSF analysis should include cytology only.

¹¹ Treatment with potassium iodide and Cytomel should be initiated 1 week prior to each ¹³¹I- omburtamab infusion in a cycle and continue until 2 weeks after ¹³¹I- omburtamab infusion in the same cycle..

¹² Thyroid protection should be initiated 1 week prior to IMP administration. See section 7.2.5 for further details.

¹³ Thyroid protection should be initiated 1 week prior to next IMP administration – this is only applicable for week 4 and not week 8. See section 7.2.5 for further details.

¹⁴ Beginning 24 hours before ¹³¹I-omburtamab administration please see section 6.1.2.

¹⁵ Given 1-2 hours prior to ¹³¹I-omburtamab administration, including oral acetaminophen/paracetamol and antihistamine (e.g., diphenhydramine), please see section 6.1.2¹⁶
Drawn and held for culture if elevated body temperature after dosing suggests infection rather than expected response to intracerebroventricular dosing.

¹⁷ Dose reduction: 50% (25 mCi) for patients < 1 of age and 33% (33.5 mCi) for patients age 1 year to < 3 years of age, respectively.

¹⁸ Non-SAE's captured from signing the informed consent form (ICF) to dosing should be recorded as medical history. AEs should be reported until 3 weeks after the last IMP administration. SAE's should be captured from signing the ICF. Starting at week 4 (for patients receiving only one cycle) and starting at week 8 (for patients receiving both cycles) only SAEs considered related to ¹³¹I-omburtamab or new onset of cancers regardless of causality should be reported.

¹⁹ Limit to therapy related to cancer.

²⁰ In case fertile women (experienced menarche prior to screening or during treatment, until week 8) are enrolled; pregnancy testing should take place at screening, at week 4 and week 8, and at follow-up at week 26.

²¹ Follow-up at week 26 (24-29 weeks after first treatment) and Long-term follow-up visits at Weeks 52, 78, 104, 130 & 156 (\pm 4 weeks) can be done at referral site.

²² If done at referral site imaging parameters as required in the Imaging Manual should be followed to the extent possible.

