9.2.2 CSF for cytology, total protein, glucose and cell count

CSF for cytology, total protein, glucose and cell count should be assessed during screening and at week 4, 8, and 26. If positive, it must be repeated within 4 weeks of the positive sampling.

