10.4 Pre-defined AEs of Special Interest

The following AEs are selected as Adverse Events of Special Interest (AESIs) based on previously experience with ^{131}I -Omburtamab and should be reported within 24 hours to sponsor:

- Neurotoxicities Grade 3 and above
- Severe infections related to placement of cerebroventricular device
- Chemical meningitis

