10.8 Reporting of Adverse Events

All events meeting the definition of an AE must be collected and reported in the eCRF. AEs occurring between Screening and first treatment must be recorded as Medical History.

SAEs and AESIs (whether serious or non-serious) should be reported both in the eCRF and on the paper clinical AE report form. SAEs must be reported from the first trial related activity after the patient has signed the informed consent until 3 weeks after last IMP administration.

Subsequent SAE reporting (occurring later than after 3 weeks after last IMP administration)

and during the long-term FU period (3 years) only SAEs considered related to the trial medication or new onset of cancers regardless of causality should be reported. The investigator should report these SAEs within the same timelines as for SAEs during the trial.

For patients withdrawn from the trial, please see section 6.9.3.

During each contact with the trial site staff, the patient must be asked about AEs, for example by asking: "Have you experienced any problems since the last contact?" All AEs, observed by the investigator or patient, must be reported by the investigator and evaluated unless specifically excluded. All SAEs and AEs leading to discontinuation of trial product either observed by the investigator or patient must be reported by the investigator and evaluated. All AEs must be recorded by the investigator on an AE form in the eCRF. The investigator should report the diagnosis, if available. If no diagnosis is available, the investigator should record each sign and symptom as individual AEs using separate AE forms. All pre-defined Adverse Events of Special Interest must be reported as SAEs.

For SAEs & AESIs, the clinical AE report form must be completed in addition to the AE form in the eCRF. If several symptoms or diagnoses occur as part of the same clinical picture, one safety information form can be used to describe all the SAEs. For all non-serious AEs, the applicable forms in the eCRF should be signed when the event is resolved or at the end of the trial at the latest.

Timelines for initial reporting of AEs:

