- Initial SAEs & AESIs: The paper clinical AE report form must be reported from site to sponsor within 24 hours of the investigator's first knowledge of the event. The paper clinical AE report form is to be sent to the designated drug safety provider by e-mail or courier. Please ensure the eCRF AE form is updated in accordance to agreed data entry timelines. New FU information available at site must be reported within 24 hours
- FU information requested from Sponsor must be replied to within three working days by using the paper data clarification form. Please ensure the eCRF AE form is updated in accordance to agreed data entry timelines.
- If the eCRF is unavailable, the concerned SAE information must be entered when the eCRF becomes available again.

Contact details for reporting:

[contact]

In emergency situations the completed safety reporting forms or pregnancy forms can be faxed to:

[contact]

Sponsor assessment of AE expectedness:

The sponsor assessment of expectedness for ¹³¹I-omburtamab is performed according to the current version of the Investigator's Brochure.

Reporting of trial product related SUSARs by Sponsor CRO

Sponsor CRO Covance Inc. will inform the regulatory authorities of any suspected unexpected serious adverse reactions (SUSARs) in accordance to regulatory requirements. Sponsor CRO Klifo A/S will notify investigators of SUSARs in accordance with local requirements. Furthermore, investigators will be informed of any trial-related SAEs that may warrant a change in any trial procedure. Sponsor CRO Klifo A/S will inform the Institutional Review Boards (IRBs)/ Independent Ethics Committees (IECs) of SUSARs in accordance with local requirement, unless locally this is an obligation of the investigator.

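### After the 3-week window, a serious complication of CSF sampling or of the access device that is judged unrelated to the drug need not be reported, although a CSF sample is scheduled at week 26

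*Combined protocol and SAP*

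**What the plan says.** **Relatedness.** Section 10.6.5 asks one binary question: "The Investigator must assess the AE as either Related or Not Related to IMP". An event counts as not related if, among other criteria, it "Is readily explained by the patient's clinical state or by other modes of therapy administered to the patient". For such events, "an alternative etiology should be stated detailing the more likely reason for AE".

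**Reporting window.** Section 10.8 requires SAEs from the first trial activity after consent until 3 weeks after the last dose, whatever their cause. For AEs, footnote 18 of Table 1 says "AEs should be reported until 3 weeks after the last IMP administration". After that, section 10.8 says "only SAEs considered related to the trial medication or new onset of cancers regardless of causality should be reported". Footnote 18 and section 6.3 set the same limit but name 131I-omburtamab instead of the trial medication. Footnote 18 starts the restriction at week 4 after one cycle and at week 8 after two.

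**Invasive sampling.** Section 9.2.2 states "CSF for cytology, total protein, glucose and cell count should be assessed during screening and at week 4, 8, and 26", with a repeat within 4 weeks if positive. Footnote 10 confirms a week-26 sample, for cytology only. Footnote 21 places that visit 24 to 29 weeks after first treatment and allows it at the referral site.

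**AESIs.** Section 10.4 lists Grade 3 or higher neurotoxicity, chemical meningitis, and "Severe infections related to placement of cerebroventricular device". These go to the sponsor within 24 hours, with no end date given. Section 10.8 adds that they are to be reported as SAEs.

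**Use of the reports.** Section 10.8 promises that "investigators will be informed of any trial-related SAEs that may warrant a change in any trial procedure".

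**The concern.** The late rule filters on relation to the drug, while the protocol continues an invasive procedure through the access device after that rule takes effect. Harm from the procedure is, by correct application of section 10.6.5, not related to the drug, so the filter removes it. The sponsor cannot tell investigators about trial-related SAEs that nobody had to send.

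The analysis carries the same problem. Section 12.4 counts an AE as treatment-emergent if it occurs after the first administration, with no upper limit. The SAE tables therefore combine a period in which all SAEs are collected with a later period in which only drug-related SAEs and new cancers are. The later part would say little about the delivery route, and nothing in the table would show that.

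Safety is a stated objective, and the drug is given only through the device. At stake is whether the safety record covers serious harm from a procedure that the trial itself schedules.

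**Working it through.** The plan states no figure on this point, so there is none to reproduce. The check is a day count followed by a trace of one event through the rules.

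**Inputs.** First dose on day 1. Second dose at week 5, day 29 (Table 1). Cycle 2 may be delayed by up to 8 weeks (section 6.1.4), counted here from day 29. The window closes 21 days after the last dose (section 10.8, footnote 18). The week-26 visit is 24 to 29 weeks after the first dose (footnote 21).

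**Week-26 visit.** Earliest: 1 + 7 × 24 = day 169. Latest: 1 + 7 × 29 = day 204.

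**Gap from window closure to the week-26 sample**

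| Case | Last dose | Window closes | Shortest gap | Longest gap |
|---|---|---|---|---|
| One cycle | day 1 | 1 + 21 = day 22 | (169 − 22)/7 = 21 weeks | (204 − 22)/7 = 26 weeks |
| Two cycles | day 29 | 29 + 21 = day 50 | (169 − 50)/7 = 17 weeks | (204 − 50)/7 = 22 weeks |
| Two cycles, 8-week delay | 29 + 56 = day 85 | 85 + 21 = day 106 | (169 − 106)/7 = 9 weeks | (204 − 106)/7 = 14 weeks |

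The week-26 sample is outside the window in every case, by 9 to 26 weeks, unless re-treatment for relapse opens a new one. A repeat under section 9.2.2 could fall up to 4 weeks later still.

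**Last treatment-period sample.** Week n starts on day 7(n − 1) + 1, so week 4 starts on day 22 and week 8 on day 50. These are the closure days for one and two cycles. A complication that appears some days after this sample is already under the restricted rule.

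**Share of sampling.** A child with two cycles has about 12 scheduled samplings: 1 at screening, 4 × 2 for PK, and one each at weeks 4, 8 and 26 (cytology and ADA taken together). One falls clearly outside the window and one at its edge; the other ten precede closure.

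**Trace of one event.** Suppose a child treated with two undelayed cycles is admitted with a culture-proven infection after the week-26 sample.

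1. Serious under section 10.2: yes, because of hospitalization.
2. Related to the drug under section 10.6.5: the last dose was (169 − 29)/7 = 20 to (204 − 29)/7 = 25 weeks earlier and another cause is evident, so not related.
3. AESI under section 10.4: the infection item concerns placement of the device, not later access. Section 6.9.3 describes chemical meningitis as culture-negative. Only an accompanying Grade 3 or higher neurotoxicity would qualify.
4. Late rule: neither related nor a new cancer, so no report is required.
5. Indirect trace: footnote 19 limits concomitant medication from week 26 to cancer therapy, so antibiotics need not be recorded either. A death would count in overall survival, but no SAE report would be required.

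**AESIs after the window.** Section 10.4 read alone gives no end date. Section 10.8 has AESIs reported as SAEs and then restricts late SAEs to related ones. Both readings are open.

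**The case against.** The case on the other side is substantial and limits the point.

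- **Cause is recorded.** A reader might infer from section 10.6.5 that causality is captured only against the drug. The documents do not support that. Not-related events need a stated alternative etiology, and Grade 3 or 4 neurologic changes are also judged against the infusion (section 9.2.10). Only the formal relatedness category is confined to the drug. The etiology entry cannot, however, recover a late event that is never reported.
- **Serious events inside the window are covered.** SAEs are collected from consent whatever their cause and summarized by system organ class and preferred term (section 12.4). That device harms stay out of the adverse drug reaction tables follows from what such a reaction is.
- **Premedication is not part of the gap.** One might infer that its harms also go unreported. Dexamethasone and the antipyretic are given around each dose, and thyroid protection stops 2 weeks after it. That exposure lies inside the window.
- **Late reporting is not nil.** One might infer that nothing about the week-26 sample is reportable. AESIs may still be, and sections 6.1.3 and 9.2.10 allow new neurologic signs without clear progression to be assumed treatment related, which would make serious ones reportable.
- **The repeat sample is uncertain.** Footnote 10 ties the repeat to the screening sample, while section 9.2.2 ties it to any positive sample. The two must be reconciled.
- **Device placement.** The trial places a device only in children who lack one (footnote 9). CSF sampling is scheduled for all.

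After all of this, a serious, non-AESI complication judged unrelated to the drug still has no late reporting requirement.

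**Conclusion.** The point holds as a narrow gap in safety reporting. It covers serious, non-AESI complications of CSF sampling or of the access device that occur after the window and are judged unrelated to the drug. The week-26 sample is always affected (barring re-treatment), and the last treatment-period sample partly. The late status of AESIs is ambiguous rather than absent.

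The number of events that would be missed cannot be estimated, because the documents give no complication rate. One case would be 1/32 = 3.1% at the planned minimum enrollment, or 1/50 = 2.0% at the maximum, if all enrolled children are treated.

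The conclusion assumes that the late rule is followed as written and that no eCRF instruction outside these documents widens it. The primary endpoint and the efficacy analyses are unaffected. The change is worth making because it is cheap, not because the documents show that harm is being missed.

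**What to change.** 1. In section 10.8, section 6.3 and footnote 18 of Table 1, add SAEs related to the access device or to a trial procedure to those reportable later than 3 weeks after the last dose.
2. In section 10.8, state that AESIs remain reportable after the window.
3. Use one term for the drug in the late rule; the text now alternates between the trial medication and 131I-omburtamab.
4. Carry the new wording into the follow-up instructions for referral hospitals, since the week-26 visit may take place there and section 6.3 says that they are not trained in the protocol.

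The cost is wording in three places and a few more SAE reports. Treatment, visits and sampling do not change. A separate yes/no item for relation to the device or a procedure, with its own table under section 12.4, would make these events easier to summarize, but it is optional because the alternative etiology is already requested.

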10.6.6 Outcome

Investigator must judge outcome of the AE by the following terms:

- Recovered
- Recovered with sequelae
 - Description of the sequelae should be provided
- Not recovered
- Death
- Unknown
 - Should only be used if patient is lost to follow-up

Instructions for reporting changes in an ongoing AE during a patient's participation in the trial are provided in the instructions that accompany the AE case report forms.

10.7 Expected side-effects related to ^{131}I -omburtamab and dexamethasone

^{131}I -omburtamab:

For detailed description, please refer to current IB.

The risks of ^{131}I -omburtamab include thyroid suppression, neutropenia and myelosuppression requiring red blood cell and/or platelet transfusions. Expected toxicities in the acute phase include the known risks associated with intraventricular infusions: headache, vomiting, and fever in the first few hours post-infusion.

Dexamethasone:

The expected toxicities of dexamethasone include lymphopenia, anemia and hyperglycemia.

10.8 Reporting of Adverse Events

All events meeting the definition of an AE must be collected and reported in the eCRF. AEs occurring between Screening and first treatment must be recorded as Medical History.

SAEs and AESIs (whether serious or non-serious) should be reported both in the eCRF and on the paper clinical AE report form. SAEs must be reported from the first trial related activity after the patient has signed the informed consent until 3 weeks after last IMP administration.

Subsequent SAE reporting (occurring later than after 3 weeks after last IMP administration)

and during the long-term FU period (3 years) only SAEs considered related to the trial medication or new onset of cancers regardless of causality should be reported. The investigator should report these SAEs within the same timelines as for SAEs during the trial.

For patients withdrawn from the trial, please see section 6.9.3.

During each contact with the trial site staff, the patient must be asked about AEs, for example by asking: "Have you experienced any problems since the last contact?" All AEs, observed by the investigator or patient, must be reported by the investigator and evaluated unless specifically excluded. All SAEs and AEs leading to discontinuation of trial product either observed by the investigator or patient must be reported by the investigator and evaluated. All AEs must be recorded by the investigator on an AE form in the eCRF. The investigator should report the diagnosis, if available. If no diagnosis is available, the investigator should record each sign and symptom as individual AEs using separate AE forms. All pre-defined Adverse Events of Special Interest must be reported as SAEs.

For SAEs & AESIs, the clinical AE report form must be completed in addition to the AE form in the eCRF. If several symptoms or diagnoses occur as part of the same clinical picture, one safety information form can be used to describe all the SAEs. For all non-serious AEs, the applicable forms in the eCRF should be signed when the event is resolved or at the end of the trial at the latest.

Timelines for initial reporting of AEs:

- Initial SAEs & AESIs: The paper clinical AE report form must be reported from site to sponsor within 24 hours of the investigator's first knowledge of the event. The paper clinical AE report form is to be sent to the designated drug safety provider by e-mail or courier. Please ensure the eCRF AE form is updated in accordance to agreed data entry timelines. New FU information available at site must be reported within 24 hours
- FU information requested from Sponsor must be replied to within three working days by using the paper data clarification form. Please ensure the eCRF AE form is updated in accordance to agreed data entry timelines.
- If the eCRF is unavailable, the concerned SAE information must be entered when the eCRF becomes available again.

Contact details for reporting:

[contact]

In emergency situations the completed safety reporting forms or pregnancy forms can be faxed to:

[contact]

Sponsor assessment of AE expectedness:

The sponsor assessment of expectedness for ¹³¹I-omburtamab is performed according to the current version of the Investigator's Brochure.

Reporting of trial product related SUSARs by Sponsor CRO

Sponsor CRO Covance Inc. will inform the regulatory authorities of any suspected unexpected serious adverse reactions (SUSARs) in accordance to regulatory requirements. Sponsor CRO Klifo A/S will notify investigators of SUSARs in accordance with local requirements. Furthermore, investigators will be informed of any trial-related SAEs that may warrant a change in any trial procedure. Sponsor CRO Klifo A/S will inform the Institutional Review Boards (IRBs)/ Independent Ethics Committees (IECs) of SUSARs in accordance with local requirement, unless locally this is an obligation of the investigator.

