9.1.2 Secondary endpoints

9.1.2.1 ***CNS/LM Progression-Free Survival (CNS/LM PFS) at 6 and 12 months***

The time frame for CNS/LM PFS will be from first treatment dose of ^{131}I -omburtamab to time of documented CNS/LM progression or death from any cause. CNS/LM PFS will be censored at last date of disease evaluation without evidence of CNS/LM progression. CNS/LM PFS at 6 and 12 months will be estimated using Kaplan-Meier methods.

9.1.2.2 ***OS at 12 months***

OS at 12 months will be estimated by Kaplan-Meier methods following the same time and censoring scheme as the primary endpoint.

9.1.2.3 ***Objective response rate (ORR)***

Response will be assessed at 6 months (week 26 visit) after the first treatment dose of ^{131}I -omburtamab as a combination of best overall partial or complete response at 5, 10, and 26 weeks. Assessments will follow the Response assessment in Neuro-Oncology (RANO) group criteria for parenchymal metastasis (Lin et al, 2015) or as defined by EANO-ESMO for leptomeningeal metastases (Le Rhun et al, 2017). The evaluation comprises MRI scans, CSF cytology, and clinical assessments. ORR at week 26 is defined as the proportion of patients with response at week 26 from the total population of patients with radiographically evaluable disease at baseline.

9.1.2.4 ***Dosimetry and PK analysis for ^{131}I -omburtamab***

An interim analysis, evaluating the dosimetry and pharmacokinetic endpoints as well as available safety and efficacy data, will be conducted on data from patients having received at least one treatment cycle1 (both dosimetry and treatment dose) prior to January 1st, 2020. Starting January 1st, 2020, no further patients will be administered dosimetry doses.

9.1.2.5 ***Performance assessment***

Since most if not all patients will have received prior crano-spinal and/or whole brain irradiation, late side effects for such previous therapies are difficult to distinguish from ^{131}I -Omburtamab inflicted toxicities in CNS. However, to evaluate gross changes in neurological

function, performance test will be conducted during screening and at weeks 26, 52, 78, 104, 130 and 156. The scales to be used are: Lansky < 16 years and Karnofsky \geq 16 years.

9.1.2.6 ***Anti-Drug-Antibodies characterization***

A quantitative assay to assess anti-drug antibodies (ADAs) will be developed. The assay will be developed and validated using “cold” labeled omburtamab (^{125}I -omburtamab).

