9.2.10 Neurotoxicity

Neurotoxicity will be assessed by the National Cancer Institute clinical neurotoxicity criteria during screening and weeks 1, 4, 5, 8, 26. All neurologic abnormalities present prior to ^{131}I -omburtamab infusions will be recorded as medical history. Any neurologic changes during the trial period which meet the criteria for Grade 3 or 4 neurotoxicity will be assessed by the trial physicians as being unrelated, possibly or probably caused by the infusion. In the absence of clear evidence progressive disease (PD), it may be assumed that new signs and symptoms are

treatment related. Any patient that develops Grade 4 neurotoxicity after the IMP infusion is to be discontinued from treatment.

Neurotoxicity also will be assessed clinically and radiographically. Assessment of cranial nerves, gross motor function and sensory function will be performed. Assessment and grading of radiographically cortical atrophy, cerebral ventricular size, white matter changes or other abnormalities will be made by a neuro-radiologist. Altered CSF flow will be interpreted by the trial nuclear medicine physicians.

Clinical neurotoxicity evaluation is to be conducted at screening and weeks 1, 4, 5, 8 and 26, as indicated in the flowchart. The radiographic assessment of neurotoxicity and disease progression (by MRI) is to be conducted at screening, weeks 4 and 8 and week 26 only.

Lansky (Karnovsky for children \geq 16 years) performance score will be analyzed to evaluate gross neurologic function and a measure of a patient's long-term function.

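### The protocol conflicts with itself on whether a late Grade 3 or higher neurotoxicity judged unrelated is reported, and any omission would understate harm

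*Combined protocol and SAP*

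**What the plan says.** **The late reporting rule.** Schedule footnote 18 ends general collection early: "AEs should be reported until 3 weeks after the last IMP administration". After that point section 10.8 restricts SAE reporting: "only SAEs considered related to the trial medication or new onset of cancers regardless of causality should be reported". Footnote 18 gives the same restriction, starting at week 4 for one cycle and week 8 for two. Section 6.3 repeats it for the 26-week follow-up.

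**The AESI rule.** Section 10.4 lists "Neurotoxicities Grade 3 and above" among three AESIs due to the sponsor within 24 hours. Section 10.8 adds: "All pre-defined Adverse Events of Special Interest must be reported as SAEs".

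**Attribution.** Section 9.1.2.5 expects most if not all patients to have had craniospinal or whole-brain irradiation. It says that "late side effects for such previous therapies are difficult to distinguish from" CNS toxicity of 131I-omburtamab. Section 9.2.10 says that without clear evidence of progressive disease "it may be assumed that new signs and symptoms are" treatment related; section 6.1.3 says much the same. Section 10.6.5 classes an event as not related if it is readily explained by the patient's clinical state "or by other modes of therapy administered to the patient".

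**The concern.** The treatment delivers radiation into the ventricles of children most of whom have already had cranial or craniospinal irradiation. Late neurological harm is therefore a safety question that the 3-year follow-up should be able to inform. If relatedness is a condition for reporting, an event put down to earlier radiotherapy leaves no adverse-event record, and no later analysis by attribution can recover it.

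The loss runs one way, because the condition can remove events but not create them. In a single-arm trial no concurrent control group would reveal it. Sites that read the rule differently would also report differently. The protocol already sets relatedness aside for new cancers, but does not clearly do so for neurotoxicity.

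**Working it through.** The documents state no figure on this point, so there is none to reproduce. The check is a comparison of texts, then the time covered, then an illustration on assumed rates.

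**1. Is a late AESI exempt from the relatedness condition?**

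- Towards no: section 10.8 has AESIs reported as SAEs, and the late window applies to SAEs. Section 10.9 groups AESIs with serious events for follow-up. The only stated exemption is for new cancers.
- Towards yes: section 10.4 sets no causality or time condition. The opening of 10.8 names SAEs and AESIs separately and includes non-serious AESIs. Its 24-hour timeline names AESIs again. Its window sentences name only SAEs.
- Both readings follow from the text, and no sentence decides between them.

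**2. Would two investigators attribute the same event alike?**

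- Sections 6.1.3 and 9.2.10 give a permissive default towards related. Section 9.2.10 uses three categories: unrelated, possibly caused, probably caused.
- Section 10.6.5 uses two categories. Prior irradiation can satisfy its not-related criterion on other therapy. It can also defeat its related criterion that medical history should not reasonably explain the event.
- A late neurological event without progression can therefore be classed either way by people who follow the text.

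**3. Time covered, for a patient followed to week 156 without re-treatment.**

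- One cycle, restricted from week 4: (156 − 4)/156 = 152/156 = 97.4%.
- Two cycles, restricted from week 8: (156 − 8)/156 = 148/156 = 94.9%.
- After the last scheduled neurotoxicity evaluation at week 26: (156 − 26)/156 = 130/156 = 83.3%. In this period the scheduled neurological measure is the Lansky or Karnofsky score (9.1.2.5), which is meant to detect gross change.

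**4. Illustration on the restrictive reading.** Let n be the number of patients (32, the planned minimum), p the true risk of a late Grade 3 or higher neurotoxicity, and q the chance that such an event is judged related. Both p and q are assumptions. Expected reports = n·p·q, and P(no report) = (1 − p·q)^n. For example, with p = 10% and q = 0.5, expected reports are 32 × 0.10 × 0.5 = 1.6, and P(no report) = 0.95^32 = 19.4%.

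| Assumed p | q = 1 (all reported) | q = 0.5 | q = 0.25 |
|---|---|---|---|
| 5% | 1.6 expected; 19.4% none | 0.8; 44.5% | 0.4; 66.9% |
| 10% | 3.2; 3.4% | 1.6; 19.4% | 0.8; 44.5% |
| 20% | 6.4; 0.1% | 3.2; 3.4% | 1.6; 19.4% |

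With the maximum of 50 patients and p = 10%, the chance of no report is 0.5%, 7.7% and 28.2% for the same three values of q.

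**5. What the analysis would show.** Section 12.4 plans adverse-event tables, including by relationship, and a summary of performance scores. It names no separate summary of neurotoxicity. It counts as treatment-emergent any event after the first administration, with no end date, so these tables would pool a period of full collection with a much longer restricted one.

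**The case against.** The strongest reply is that a specific AESI rule overrides a general SAE window, so late Grade 3 or higher neurotoxicity is reported whatever its cause. Section 9.2.10 supports this: it has any Grade 3 or 4 neurological change during the trial period assessed, with unrelated as one possible answer. This reading is reasonable, and it defeats the inference that such events are certain to be reported only if judged related. It does not remove the conflict, because 10.8 makes AESIs reportable as SAEs and exempts only new cancers.

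A reader might also infer that the protocol gives two opposite default attributions. It does not. The only default points towards related. Section 10.6.5 gives criteria, with a threshold of a reasonable possibility, and it asks for an alternative cause even for events classed as possibly related. An event that is hard to attribute is also not readily explained by something else. What stands is that its criteria and its two-category scale do not match 9.2.10.

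Week 26 is not a good example of the gap. A clinical neurotoxicity evaluation and an MRI take place then regardless of causality. After week 26 the safeguards are thinner: performance scores, physical examination as clinically indicated (9.2.8), and records of disease progression.

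Referral hospitals that supply follow-up data are not trained in the protocol. However, the trial investigator coordinates collection (6.3) and causality is the investigator's judgement (10.6.5), so this adds little.

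Nor do the documents show that late events would be hidden from the data monitoring committee. What it receives is set in its charter, which is not among them.

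Finally, all-cause reporting would mix effects of the study drug, earlier irradiation, later anti-cancer therapy and progression. That is a real cost, and recorded covariates answer it only in part.

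**Conclusion.** The concern holds as an unresolved conflict in the reporting rules, not as a demonstrated loss of events. Sections 10.4 and 10.8 do not settle whether a late Grade 3 or higher neurotoxicity judged unrelated must be reported. If the restrictive reading is applied, reporting depends on an attribution that the protocol calls difficult, and the bias can only be towards understating harm.

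The restriction covers 95 to 97% of the 156 weeks by footnote 18. These are shares of calendar time for a patient who completes follow-up, not shares of events. Re-treatment after relapse would move the last dose and reopen full reporting. The rates in the illustration are assumed; it shows only that, with 32 patients, a moderate degree of filtering could make a report of no late events fairly likely. The point does not touch the primary survival endpoint. It is worth correcting because the correction is specific and cheap.

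**What to change.** 1. In section 10.8, footnote 18 and section 6.3, state that Grade 3 or higher neurotoxicity, as an AESI, is reported regardless of causality through week 156, on the same footing as new cancers.
2. For each such event, record the investigator's attribution, CNS/LM progression status and any subsequent anti-cancer therapy as data, none of them a condition for reporting.
3. Use one causality scale in sections 9.2.10 and 10.6.5, and say how the permissive default for neurological signs fits with the general criteria when the patient has had prior irradiation.
4. In section 12.4 and the SAP, add a summary of late Grade 3 or higher neurotoxicity, overall and by attribution.

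The cost is protocol wording, a few data fields and some extra AESI reports at the existing 6-monthly contacts. Some of those reports will concern progression or later therapy, and the recorded fields will separate them only in part. No treatment rule changes.
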